3. DLQI
4. ItchyQoL
5. Leuven Itch Scale
6. Static Patient Global Assessment of Itch Severity (sPGAIS)
7. Patient Global Impression of Change in Itch Severity (pGICIS)
8. Caregiver Global Impression of Change in Itch Severity (cGICIS)
9. PROMIS scales – Pediatric version for participants <18y
10. Itch Controlled Days Questionnaire

If a participant is unable to access REDCap, these questionnaires will be administered over the phone. Instruments requiring visual analog scale (VAS), such as the Leuven Itch Scale, will be mailed, faxed, or emailed to enable the participant to physically complete the VAS.

Participant Instruments requiring visual analog scale (VAS), such as the Leuven Itch Scale, will be mailed, faxed, or emailed to enable the participant to physically complete the VAS.

9.C.iv. Reminders and Instructions:

Participants will be instructed to mail back their diaries, remaining serlopitant, and empty bottles.

9.C.v. Dispensing Serlopitant:

Additional serlopitant will be dispensed pending investigator review of safety labs.

9.G. Early Termination Protocol:

9.G.i. Early Termination in Double Blind Phase:

If a participant terminates study participation early, while in the double-blind phase, they will be asked to return to Stanford for an Early Termination visit.

Study staff will review the reason for early termination and investigators will facilitate medical follow-up as needed. Study staff will review adverse events, changes to concomitant medications, diaries, medication adherence, and will administer questionnaires.

We will request that the participant have safety labs drawn.

They will be instructed to return study diaries, remaining medication, and empty medication bottles.

If the participant is willing to come to Stanford, we will perform vital signs, physical examination, target wound assessment and photographs, and ECG.

9.G.ii. Early Termination in Open Label Phase:

If a participant terminates study participation early, while in the open label phase, study staff will call the participant for an Early Termination call.

Study staff will review the reason for early termination and investigators will facilitate medical follow-up as needed. Study staff will review adverse events, changes to concomitant medications, diaries, medication adherence, and will administer questionnaires.

We will request that the participant have safety labs drawn.

They will be instructed to return study diaries, remaining medication, and empty medication bottles.

9.H Modification to Study Procedures Due to COVID-19

Due to the pandemic caused by the COVID-19 virus, at the discretion of the Principal Investigator, it may be necessary for participants and staff welfare that study visits under this protocol are conducted remotely. This may apply to both initial enrollment visits, alongside follow up visits. All remote study visits will be conducted securely using HIPAA compliant telemedicine tools, including but not limited to the integrated EPIC telemedicine system, ensuring patient confidentiality and data security. As a consequence of conducting remote study visits, it may not be feasible to conduct all study related procedures as documented in the schedule of events.

As such, the following modifications to these procedures may be required:

9.H. i. Consent: Potential participants will be provided with advanced copies of the informed consent form either by mail or email. During the remote combined screening/baseline visit, participants will be consented remotely and will then return the signed consent form by mail or secure email. Participants may sign consent electronically via secure database.

9.H. ii. Physical Exam: Examination elements that are feasible will be conducted remotely using video streaming. All practical attempts will be made to obtain physical examination records from the last 12 months.

9.H. iii. Vital Signs, Height & Weight: These events will be omitted during remote study visits, as it is not feasible to conduct these measurements remotely. As these do not contribute to the eligibility assessment nor

adversely affect Serlopitant's safety profile, they are not necessary for study participation. If there are concerns about participant's medical stability, investigators may refer patients to their primary care physicians or other providers for their assessment prior to making determination of eligibility for the study.

9.H. iv. *Electrocardiogram (ECG)*: This test will be omitted during remote study visits to avoid potential harm to the participant, as ECG leads will tear their fragile skin and result in painful wounds. At Stanford, we have developed a protocol to perform ECGs on EB patients safely by knowledgeable, specifically trained personnel. Therefore, we will only perform ECGs at in-person visits at Stanford. 31 patients previously completed Serlopitant in studies where ECGs were not performed.

9.H. v. We will schedule lab draws and urine tests at local labs convenient for the participant. Labs and urine test will ideally be drawn within 72 hours of remote visit.

9.H. vi. *Photographs*: A subset of participants with target wounds as defined in the protocol will be asked to securely send digital photos during or after combined screening/baseline visit (or follow up visits as applicable) using Tissue Analytics smart phone application or secure email. Participants will be instructed on how to take these photos, which will include a ruler for measurement. Measurements will be taken from these photos and used for analysis.

9.H. vii. *Serlopitant Drug Dosing & Dispensing*: Serlopitant dosing instructions will be provided during the combined screening/baseline visit as usual. Study drug will be dispensed only after consent has been obtained, eligibility verified, and participant randomized to receive placebo or active drug. Medication will be shipped to patients overnight at ambient temperature. Adult signature will be required for delivery.

10. Statistical Analysis Plan:

10.A. Randomization Plan

Participants who are determined to be eligible and proceed to randomization will be assigned a unique randomization code. The randomization key will be held by the trial statistician or a blinded member of the study team. Unblinding for each participant will occur for each participant once they complete the randomized phase AND their data is locked, or if a trial participant experiences an adverse event or any other significant safety concern where the investigator deems unblinding of that individual necessary for participant safety. This unblinding strategy was chosen to facilitate participants' decisions on whether to participate in the open label phase. Given that the critical endpoints in this trial are participant-reported, the investigators deemed that equipoise would be maintained under these circumstances.

In order to prevent operational bias (which could theoretically arise should interim aggregate analysis be performed), individual participants' itch scores will be data locked upon completion of the randomized phase and accessible thereafter only to their assigned coordinators and/or coordinators tasked with auditing a participant's data for data integrity. Investigators will not be provided REDCap access for aggregate analysis until the final participant has completed the randomized phase of the trial.

In order to balance allocation of more severe EB subtypes, participants with either dystrophic EB (including both dominant and recessive types) or junctional EB will receive a separate set of randomization codes for binary stratification of these more severe EB subtypes among the two treatment arms.

10.B. Sample Size Calculation:

This Phase 2 clinical trial involving at least 40 participants is powered to determine statistically significant differences in the placebo (N=20 participants) vs. 5 mg (N=20 participants) groups. The sample size is powered to detect moderate differences in the proportion of responders (3-point NRS decrease in itch) between the active and placebo groups.

Results from our Phase 2 trial showed that 43% of active participants were responders vs. only 14% in placebo were responders (1 out of 7). Using a one-sided Fisher's exact test, our power calculations show that we need to enroll a total of 40 participants (1:1) to have 80% power to detect a difference of 50% vs 10% responder rates in active and placebo groups, respectively.

	Responder	None	Total
Active	10	10	20
Placebo	2	18	20
Total	12	28	40

Fisher's exact test

The two-tailed P value equals 0.01

Because itch is subjective and varies daily, participants will be asked to keep an itch diary nightly before bedtime when itch has been reported to be the worst. According to recent psychometric studies, the important difference for clinical improvement of chronic pruritus ranks between a drop of 2 to 3 points on the NRS^{78,8,12}. This trial is powered to be able to detect this level of clinically meaningful reduction in itch.

10.C. Statistical plan for efficacy endpoints:

The proportion of participants achieving 2, 3, and 4-point reductions in average daily NRS with serlopitant at the end of 8 weeks of active treatment will be compared to placebo using Fisher's Exact test. A similar approach will be utilized to compare the proportion of participants achieving at least a 30% or 50% reduction in itch as measured by NRS from baseline at 8 weeks.

We will also measure continuous change in average daily NRS and worst-itch NRS score by group over time. For each participant, we will plot their average itch scores over time before and after drug intervention. For each dosage group, we will use linear regression methods with mixed effects (GLM, SAS) to track the change in itch in each of the groups from baseline.

Furthermore, we will evaluate monthly change in median NRS itch scores by group as compared to baseline, which will enable evaluation of durability through assessment of NRS itch scores at month 3 of washout.

Primary and secondary endpoints will be performed on an intention to treat basis. This study will provide the effect size, standard deviation and range of itch scores in EB participants in order to properly power a phase 3 trial.

11. Safety Assessment and Monitoring

11.A. Pregnancies and Contraception Requirements for Females

For the purposes of this study, a female of childbearing potential is defined as any female who has experienced menarche and is pre-menopausal, unless permanently surgically sterile (e.g., hysterectomy, bilateral salpingectomy, bilateral oophorectomy). A postmenopausal state is defined as no menses for 12 months without an alternative medical cause in a previously menstruating female. We note that many adolescents with severe subtypes of epidermolysis bullosa have may significantly delayed age of menarche.

For the purposes of this study, all female participants of childbearing potential must use highly effective contraception (i.e. pregnancy prevention method with a failure rate of <1% per year) from the time of the Screening visit until 2 weeks after the last dose of study drug. This includes the use of one or more of the following acceptable methods:

1. Surgical sterilization (e.g., bilateral tubal occlusion or ligation, hysterectomy, bilateral salpingectomy, bilateral oophorectomy).
2. Total (as opposed to periodic or cyclic) abstinence from heterosexual intercourse, only if planned for the entire duration of the study period and consistent with the preferred and usual lifestyle for the participant
3. Hormonal contraception associated with consistent inhibition of ovulation; these may include (but are not necessarily limited to) oral, intravaginal, implantable, injectable, or transdermal delivery methods
4. Intrauterine device/system
5. Exclusive (sole) monogamous intercourse with a sterilized (i.e., vasectomized) or otherwise non-fertile (e.g., castrated) male partner; the male partner must have received medical assessment of the surgical success

Any pregnancy occurring in a female participant or the female partner of a male participant, from the first study drug administration through the required follow-up visit will be reported within 24 hours of the investigator's awareness of the pregnancy. Any pregnancies that occur will be dated for time of conception through coordination with participants' family medicine or obstetrics provider based on ultrasound findings, quantitative serum BHCG results, last menstrual period, physical examination, and timing of coitus.

The investigators will follow the pregnancy to delivery or other pregnancy outcome. Pregnancy in a female clinical trial participant or female partner of a male clinical trial participant is not an SAE per se.

Any abnormal pregnancies that occur during the trial will be flagged as a serious adverse event and all available information will be captured as part of the CRF. Abnormal pregnancies include (but are not limited to): spontaneous abortion, missed abortion, benign hydatidiform mole, blighted ovum, fetal death, intrauterine death, miscarriage, and stillbirth).

Complications during pregnancies will be reported as such even if they occur after the Follow-up visit. All exposed infants will be followed and assessed at birth. Any congenital anomalies/birth defects will be recorded in the CRF and reported as SAEs.

11.B. Study Drug Discontinuation

Participants should be discontinued from study drug treatment in any of the following situations:

1. A female participant desires to become pregnant at the current time, stops contraception, expels her intrauterine device/implant, or becomes pregnant
2. A female participant has new breast findings (e.g. a palpable mass or abnormal mammography, discharge), or has abnormal vaginal discharge or bleeding
3. The participant decides to discontinue study drug treatment, or withdraws consent from the study
4. The participant receives a strong CYP3A4 inhibitor
5. Any medical condition that may jeopardize the participant's safety if study drug is continued, in the investigator's opinion; this may include the development of persistently (2 successive occasions) abnormal thyroid function tests (TSH >10, or TSH > 5 with low free T4; TSH <0.1, or TSH < 0.4 with high free T4); abnormal morning prolactin >100 ng/mL, cortisol, or corticotropin levels; or signs and symptoms of adrenal insufficiency. Participants with abnormal endocrine assessments will be referred to an endocrinologist for evaluation, which may include repeat laboratory assessment for participants with abnormal thyroid levels every 4-6 weeks until the abnormalities resolve.
6. Discontinuation is deemed to be in the best interest of the participant, in the investigator's opinion, including evidence that the participant does not meet inclusion/exclusion criteria intended primarily for safety reasons, or a persistent lack of adherence to study procedures

11.C. Definition of Adverse Events:

An adverse event (AEs) or suspected adverse reaction is considered “serious” (SAE) if, in the view of the investigator, it results in any of the following outcomes: Death, a life-threatening adverse event, inpatient hospitalization or prolongation of existing hospitalization, a persistent or significant incapacity or substantial disruption of the ability to conduct normal life functions, or a congenital anomaly/birth defect. Important medical events that may not result in death, be life-threatening, or require hospitalization may be considered serious when, based upon appropriate medical judgment, they may jeopardize the participant or participant and may require medical or surgical intervention to prevent one of the outcomes listed in this definition.

The Principal Investigator will provide oversight on monitoring safety/AEs/SAEs at this site. For data safety monitoring, the principal investigator, co-principal investigator, and any sub-investigators will formally meet monthly to review all new AEs, SAEs, and any safety concerns that arose in the past month.

11.C.i. Criteria for Unanticipated Problems:

The investigators as a group will assess whether the AE represents an unanticipated problem (UP) based on the following criteria:

Events (internal or external, deaths, life-threatening experiences, injuries, or other) occurring during the research study, which in the opinion of the PI meet ***all*** of the following criteria:

- a) Unexpected** in terms of nature, severity, or frequency, given (a) the research procedures described in the protocol-related documents, and (b) the characteristics of the participant population being studied; **AND**
- b) Related to participation in the research** or there is a reasonable possibility or likelihood that the incident, experience, or outcome may have been caused by the procedures involved in the research; **AND**
- c) Harmful** that the research places participants or others at a greater risk of harm (including physical, psychological, economic, or social harm) than was previously known or recognized.

11.D. Reporting Adverse Events:

11.D.i. Reporting UPs:

If the investigator determines that the AE represents a UP, the investigator will report the AE to the IRB **within 10 working days** from when the PI learns of the event.

If the adverse event does not qualify as a UP, the adverse event should be reported at continuing review.

11.D.ii. Reporting SAEs:

Unexpected deaths or life-threatening experiences **related** to the research will be reported to the IRB **within 5 working days** from PI learning of event.

Reporting any unexpected fatal or life-threatening suspected adverse reactions to the FDA will occur **no later than 7 calendar days** after initial receipt of the information.

Reporting any (1) serious, unexpected suspected adverse reactions, (2) findings from other clinical, animal or in-vitro studies that suggest significant human risk, and (3) a clinically important increase in the rate of a serious suspected adverse reaction to the FDA and all investigators will occur **no later than 15 calendar days** after determining that the information qualifies for reporting.

11.D.iii. Reporting AEs:

In this study, the occurrence of any AE from the time of informed consent until 4 weeks after the last dose of study drug will be reported to the Stanford IRB and the FDA.

Submission of annual progress reports will occur within 60 days of the anniversary of the date that the IND went into effect (date that clinical studies were permitted to begin).

11.E. Data Monitoring Plan:

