with any EB subtype. Although the 14 participant trial was only powered to detect large differences in numeric rating scale (NRS) itch scores, we observed a small magnitude reduction in NRS itch score over time in favor of serlopitant relative to placebo (0.08 point/week comparative reduction) although this difference did not meet statistical significance ($p=0.11$). This was equivalent to a 0.64-point reduction in the NRS itch score (rated 0-10) by the end of the active treatment period. In post-hoc analysis, we found a significant majority of participants in the serlopitant arm (86%) experienced at least a 1-point reduction in NRS score by end of treatment. More participants in the active group (43% vs. 14%) achieved at least a 3-point reduction in NRS itch score by the end of treatment as compared to placebo, although this was not statistically significant ($p=0.35$). Serlopitant was well tolerated, with no new safety signals observed.

6. Study design:

This is an investigator-initiated, single-center, randomized, double-blind, placebo controlled, parallel arm trial evaluating the effects of serlopitant at 5 mg by mouth daily on EB-related itch. Eligible participants must have a clinical diagnosis of EB and average daily pruritus rated at least 5 based on a 0-10 Numeric Rating Scale (NRS) persistent for at least 6 weeks.

We aim to recruit at least 40 participants, age 13 and older, of all EB subtypes. Participants will be assigned to placebo or serlopitant in a 1:1 ratio. Participants randomized to serlopitant will receive a loading dose of serlopitant 15 mg PO once, followed by serlopitant 5 mg PO daily for 2 months. This dosing regimen is identical to that investigated during our pilot phase 2 trial.

After completing the double-blind phase of the trial, all participants will undergo one month of wash-out before being offered the option of participating in an open label extension phase with serlopitant 5 mg PO daily for continued monitoring of toxicity and efficacy. This extension phase will be 12 months for participants enrolled prior to May 2020, and 3 months for participants enrolled after May 2020, due to drug availability.

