Due to the potential pain and skin injury that can be incurred with travel for participants with more severe EB subtypes, this trial is intentionally designed to minimize the number of in-person clinic visits through use of home itch diaries and phone follow-up, as recommended by the FDA in their EB-specific guidance document.⁴

7. Efficacy Endpoints:

Based on the data from our pilot study, the primary statistical endpoint will be the proportion of participants who achieve at least a 3-point reduction in average daily NRS itch severity from baseline at the end of the two-month double-blind phase.

Secondary endpoints will include:

1. Comparative weekly change in daily worst-itch NRS during the double-blind phase
2. Safety, as measured by adverse events during the course of the double-blind and open label phases of the trial. These will also include changes in ECG parameters and safety labs following drug exposure.
3. Comparative weekly change in average daily NRS itch severity during the double-blind phase
4. Proportion of participants who achieve at least 2 and 4-point reductions in average daily NRS itch severity from baseline at the end of the double-blind phase
5. Proportion of participants who achieve at least a 30% or 50% reduction in average daily NRS itch severity from baseline at the end of the double-blind phase
6. Change in participant-reported outcomes of global assessment of change in itch and overall improvement as measured by static participant assessment of itch, participant global assessment of change in itch severity, and caregiver global assessment of change in itch severity.

The Stanford EB Itch Survey also captures additional measures related to symptoms during dressing changes, sleep quality, and other quality of life measures which may be explored.

Additional exploratory endpoints will revolve around mean comparative change in wound surface areas, comparative change in NRS itch severity at target wounds, and the change in median NRS score by group from baseline at month 1, month 2, and month 3.

We will also assess participant and caregiver perceived change in wound size and number, and pain as measured with the Wong-Baker FACES⁵ scale, and changes in quality of life assessed with ItchyQoL,⁶ and the Dermatology Quality of Life Index (DLQI).⁷

Further exploratory analysis comparing multiple pruritus-related instruments will be explored to determine the most appropriate measures of pruritus for this participant population.

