3. DLQI
4. ItchyQoL
5. Leuven Itch Scale
6. Static Participant Global Assessment of Itch Severity (sPGAIS)
7. Participant Global Impression of Change in Itch Severity (pGICIS)
8. Caregiver Global Impression of Change in Itch Severity (cGICIS)
9. PROMIS scales – Pediatric versions for participants <18y
10. Itch Controlled Days Questionnaire

If a participant is unable to access REDCap, these questionnaires will be administered over the phone. Instruments requiring visual analog scale (VAS), such as the Leuven Itch Scale, will be mailed, faxed, or emailed to enable the participant to physically complete the VAS.

9.C.iv. Reminders and Instructions:

Participants will be reminded to comply with completing their itch journals and medication.

Participants will be instructed to mail back their month 1 itch diaries once they receive their new itch diaries (not applicable if participant has chosen to utilize a REDCap based online diary). Additional medication will be dispensed pending acceptable safety labs and mailed to participants along with new Month 2 itch diaries (if participant has chosen physical diary). Participants will be asked to set aside any medication from their month 1 medication bottle and seal the bottle to be returned at their next visit and begin month 2 treatment from the new bottle.

9.D. Month 2 Study Visit:

At 60 days following initiation of study medication (+/- 14 days), participants will return to Stanford for a follow up clinic visit.

Participants will be queried for any adverse events and changes to concomitant medications or wound dressing regimen. These will be assessed by investigators. Menstrual diaries will be collected and reviewed. Participants will be asked to submit their nightly itch diary (NRS), along with any unused medications from the prior two months of treatment for assessment of medication adherence.

Participants will specifically be asked about any symptoms of adrenal insufficiency (e.g. fatigue, abdominal pain, dizziness, etc.). Participants who report symptoms concerning for adrenal insufficiency will be evaluated with instructions to follow-up urgently with their primary care provider for further evaluation, which should include an AM cortisol. If this is abnormal, the participant will be referred urgently to endocrinology for further evaluation including cosyntropin stimulation testing.

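### Section 10.A does not tie routine unblinding to a visit, so participants may know their arm before they report Month 3 wash-out itch

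*Combined protocol and SAP*

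**What the plan says.** Section 10.A sets two conditions for routine, participant-by-participant unblinding: "Unblinding for each participant will occur for each participant once they complete the randomized phase AND their data is locked". It then says that each participant's "itch scores will be data locked upon completion of the randomized phase". The aim is to help participants with their "decisions on whether to participate in the open label phase". A separate clause allows unblinding of an individual for safety.

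The term *randomized phase* occurs three times, all in 10.A, and is never linked to a visit or a study day. Other sections speak of a double-blind phase:

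- Section 6 places the wash-out after the double-blind phase: "all participants will undergo one month of wash-out before being offered the option of participating in an open label extension phase".
- Section 7 takes the primary endpoint "from baseline at the end of the two-month double-blind phase".
- Section 9.D sets the Month 2 visit: "At 60 days following initiation of study medication (+/- 14 days"). The treatment diary is handed in at that visit.
- Section 9.E puts the Month 3 call 30 days, plus or minus 14, after the double-blind phase is completed.
- The Schedule of Events, as extracted, runs its double-blind header over four columns: Baseline, Month 1, Month 2 and Month 3.

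Itch is still an outcome at Month 3. Section 7 lists as exploratory "the change in median NRS score by group from baseline at month 1, month 2, and month 3", and section 10.C uses the Month 3 scores to judge durability.

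**The concern.** Itch NRS is a self-report, and a participant who knows the assigned arm may score differently. Someone who learns that they took placebo, or that active drug has been stopped, may rate wash-out itch in light of that knowledge. A by-group difference at Month 3 would then mix persistence of effect with expectation, and no analysis can undo a disclosure once made.

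Section 10.A does not ask for the disclosure date to be recorded. If some participants were told before Month 3 and others after, the two sets of scores might not be separable later. The daily wash-out diary and the Month 3 questionnaires, including the global impressions of change, are exposed in the same way, although no Month 3 between-group analysis is specified for the questionnaires.

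**Working it through.** The plan gives no figure for this interval, so the check sets the two readings side by side and derives the interval from the visit windows.

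**Inputs**
- Month 2 visit: day 60 ± 14 from first dose (section 9.D).
- Month 3 call: 30 ± 14 days after the double-blind phase is completed (section 9.E).
- Assumption: the double-blind phase ends at the Month 2 visit.

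**Visit timing**
- Month 2: 60 − 14 = day 46 to 60 + 14 = day 74.
- Gap from the end of the double-blind phase to the Month 3 call: 30 − 14 = 16 to 30 + 14 = 44 days, nominal 30.
- Month 3: 46 + 16 = day 62 to 74 + 44 = day 118, nominal 60 + 30 = day 90.

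**Reading A: the randomized phase is the two-month double-blind phase of sections 6, 7 and 9.E.** Itch scores are locked on its completion, and the treatment diary is in hand at Month 2. If lock and disclosure fall on that day, the time with the arm known before the Month 3 call equals the gap: 16 to 44 days, nominal 30. Any delay in locking shortens it. The documents give no length for such a delay, so these figures are upper limits.

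**Reading B: the randomized phase is the Schedule's double-blind block, which includes Month 3.** Lock and disclosure follow the Month 3 assessments. Time with the arm known before them: 0 days.

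**Does anything in the text choose between A and B?**
- The wording on the lock does not: it refers to completion of the same undefined phase.
- The stated purpose does not: a disclosure at Month 2 or after Month 3 would in either case precede the open-label offer, which section 6 places after the wash-out.
- Section 9.G provides for early termination only in the double-blind or the open-label phase. That leans towards B, because otherwise the wash-out belongs to neither, but it does not define the term.
- No section says that participants stay blinded through the wash-out.

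**Which outcomes lie after the earliest routine disclosure?** The primary endpoint and the other responder proportions are taken at the end of the two months, so a participant's own data for them are complete before any routine disclosure. The Month 3 median NRS by group comes later and is exposed under A.

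**The case against.** The best case for the plan is that reading B is the natural one. Unblinding exists to inform the open-label decision, that option is offered only after the wash-out, and the Schedule puts Month 3 under the double-blind header. The data to be locked could well include the Month 3 scores that 10.C analyses, and those cannot be locked before Month 3. The strategy was also deliberate: 10.A says that equipoise was considered, restricts access to locked scores, and withholds aggregate access from investigators until the last participant completes the randomized phase.

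Much of this stands. Reading B may be what was intended, and the lock is not without an anchor, since itch scores are locked when the phase completes. But the intention is not written down, and the body text supports reading A. The access limits guard against interim aggregate analysis; they do not govern what the participant knows. The argument that the critical endpoints are participant-reported does not protect reports made after disclosure.

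A reader might infer more: that the plan requires unblinding at Month 2, or that the primary result is compromised. The documents support neither. Reading B is open, and the two-month endpoints precede any routine disclosure.

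**Conclusion.** The point holds as an ambiguity with a limited consequence. Section 10.A permits, but does not require, routine unblinding before the Month 3 self-reports. The possible exposure is up to 16 to 44 days (nominal 30) on the body-text reading and 0 days on the Schedule reading. The upper figures assume that the phase ends at the Month 2 visit and that lock and disclosure occur on the same day. The Schedule reading rests on the header layout as extracted.

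The named outcome at risk is exploratory, with other wash-out self-reports alongside it. The size of any bias in the Month 3 scores cannot be computed from the documents. The matter deserves consideration because a disclosure cannot be reversed and the remedy is cheap; it is no reason to doubt the primary analysis.

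**What to change.** In section 10.A, define the randomized phase by visit and add a sentence such as: *Routine unblinding of a participant occurs only after that participant's Month 3 wash-out diary and questionnaires have been collected and locked, and before the open-label decision.* Leave the safety-unblinding clause unchanged. Reconcile the Schedule header over Month 3 with sections 6 and 9.E.

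If earlier release is kept, record each participant's disclosure date and label the Month 3 results as potentially unblinded.

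Cost: on the body-text reading participants learn their arm about one month later; on the Schedule reading the disclosure time does not move. Open-label dispensing, which the Schedule as extracted allows from Month 3, may have to wait for the Month 3 lock, and mailed paper diaries could add to that wait. Section 9.F.i accepts Month 3 labs drawn within 4 months of the open-label baseline, so a short wait should not need another blood draw. The sponsor's aim is kept, because the arm is still known before the open-label decision described in sections 6 and 9.F.

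A separate minor wording point: 10.A lets the randomization key be held by the statistician or by a team member described as blinded. Someone who holds the key cannot be assured to be blinded, so the key should stay with the statistician.
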